#### **4.Design, procedures, materials and methods:**

Use a level of detail similar to what would be used when submitting an article for publication in a peer reviewed journal. Explain the study procedures, data collection, and analysis process. Please define terms and explain concepts which might be confusing to reviewers who are not expert in the area of the study. If a formal protocol for the study exists, page references to the protocol are acceptable.

Patient selection. Patients with medically refractory epilepsy are referred to DHMC for surgical evaluation. The first stage of the evaluation includes inpatient video EEG monitoring, epilepsy protocol MRI, and a neuropsychological evaluation. Following the initial evaluation, each patient's case is discussed in the epilepsy surgery conference. The conference is attended by all Dartmouth epilepsy neurologists and neurosurgeons. A consensus among all physicians is reached regarding further evaluation. Approximately 50% of patients require intracranial EEG (iEEG) recording prior to epilepsy surgery. If a patient requires iEEG, the strategy for the exact type of electrode implantation is determined at the same surgical conference. Subsequently, the need for iEEG monitoring is discussed with the patient in the outpatient clinic. Patients who meet clinical indication for iEEG recording will be asked to participate in the research study. If the patient agrees, certain standard electrodes will be substituted with the dual micro-macro electrodes during the iEEG recording.

Electrodes. Ad-tech is the largest manufacturer and supplier of intracranial electrodes for use in epilepsy surgery. Ad-tech standard macroelectrodes have been used at Dartmouth-Hitchcock Medical Center since 1992 in hundreds of iEEG cases. In addition to macroelectrodes, Ad-tech currently manufactures two types of dual macro-micro electrode systems that will be used in the study. The appropriate type of electrode system will be determined by the study team.

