**Cognitive Tasks.** Patients who agree to participate in microelectrode studies may be asked to participate in a study which involves a cognitive task. Each task will be specifically designed to elicit a specific cognitive function important to testing of the regions where electrodes are implanted. The task could be a memory task, such as remembering of word pairs if electrodes reside in the hippocampus. The task may involve perception of facial emotion, mimicry of facial movements, mimicry of planned movements, smell appreciation, taste appreciation, appreciation of disgust, or visual spatial analysis. The type of task that a patient gets will depend on the region of the brain that is implanted by the microelectrode.

**Data Analysis.** Data on neuronal discharge characteristics will be recorded using the 64 Chanel Digital Lynx system running Cheetah software. The characteristics of fast ripples, and the data on neuronal firing characteristics during specific cognitive tasks will be exported to Matlab software for statistical analysis. Data analysis will be done by either the study team at DHMC/Dartmouth College, or by collaborators at Columbia University.

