**7. Statistical Methods and Review Statement:**

**a)** Specify the primary endpoint, as well as other endpoint(s).

The primary hypothesis is that high oscillations (fast ripples) occur in epileptogenic cortex and are absent in non-epileptogenic cortex. Our secondary hypothesis is that single unit activity recorded from various electrode positions in the brain will correlate with specific cognitive tasks.

**b)** State the statistical analysis plan, including all hypothesis tests (e.g., t-test, chi-square), and estimation methods related to the primary endpoint. If a formal protocol for the study exists, page references to the protocol are acceptable.

The recording of high frequency oscillations will require only basic statistical analysis using chi-square testing. The analysis of neuronal discharge characteristics and temporal association with specific cognitive tasks will be done using Matlab.

**c)** Justify the sample size, using the concepts of power, type I error, and effect size if applicable. If a formal protocol for the study exists, page references to the protocol are acceptable.

We are planning to enroll up to 50 patients over an extended period of time. The power calculations and effect size, will depend on the cognitive task applied in the individual patient for the specific electrode array.

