## **12. Timetables:**

**a)** Indicate length of participant involvement in the study: **Each participant will be enrolled into the study for the duration of their iEEG monitoring, this is an inpatient admission of less than two weeks.**

**b)** Estimate how long it will take to enroll enough participants to complete this study: **This will be an ongoing study. We think we can enroll 2-3 patients per year.**

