**16. Adequacy of Resources to Protect Subjects:**

**a)** Investigator (including co-investigators) has sufficient time to conduct and complete the research.

Yes  No

**b)** Adequately qualified (including experience, training, supervision, and familiarity with the protocol) staff are available for this research.

Yes  No.

**c)** Describe availability of psychological, social, or medical services, which include counseling or social support services, that may be required as a consequence of research participation.

Patients are routinely evaluated by neuropsychologists as part of routine work-up. As subjects will be inpatients during their participation in the study, epilepsy, neuropsychiatry, and psychology services will be available.

**d)** Describe psychological, social, or medical monitoring, ancillary care, equipment needed to protect participants (e.g. close proximity to resuscitation equipment or a plan for monitoring of emotional state during study procedures).

The study will be conducted inside the Epilepsy Monitoring Unit (EMU) at DHMC. This unit is specifically equipped to deal with complications of epilepsy and epilepsy surgery. The unit has continuous video EEG monitoring, meets safety standards for operating an EMU, has specially trained and qualified nurses who are able to treat seizures.

e) Describe other resources needed for the protection of subjects in the conduct of this research (e.g. language translation services).

None

**f)** Explain how the investigator has access to a population that would allow recruitment of the required number of subjects.

Patients who have medically refractory epilepsy are referred to the DHMC Epilepsy Center for surgical evaluation. Each year, between 10-15 intracranial EEG studies are performed. Patients will be recruited from among all patient who meet the inclusion criteria. We anticipate that 5-8 patients per year will be recruited to participate in the study.

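### Section 7b names only chi-square for a hypothesis that predicts no positives in one class; if positive sites are few, the uncorrected test can mislead, and no exact test is fixed in advance

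*Combined protocol and SAP*

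**What the plan says.** Section 7a gives the primary hypothesis: "The primary hypothesis is that high oscillations (fast ripples) occur in epileptogenic cortex and are absent in non-epileptogenic cortex". For its analysis, 7b says "The recording of high frequency oscillations will require only basic statistical analysis using chi-square testing". It does not say whether this means the Pearson statistic or a continuity-corrected one. It has no rule for small expected counts, no exact test, no significance level and no interval estimate, although the form's question asks for estimation methods.

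The size of the table is open:
- Section 7c gives a ceiling, "We are planning to enroll up to 50 patients over an extended period of time", and leaves power to the cognitive tasks: "The power calculations and effect size, will depend on the cognitive task applied in the individual patient for the specific electrode array". Neither statement sizes the fast-ripple comparison.
- Section 4 says that "certain standard electrodes will be substituted with the dual micro-macro electrodes during the iEEG recording", without saying how many per patient. It also mentions a 64-channel recorder ("Data on neuronal discharge characteristics will be recorded using the 64 Chanel Digital Lynx system running Cheetah software"), but no section says whether the unit counted is a channel, an electrode, a region or a patient.
- Accrual is stated twice and differently: "We think we can enroll 2-3 patients per year" in section 12b and "We anticipate that 5-8 patients per year will be recruited to participate in the study" in section 16f.

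**The concern.** The chi-square p-value is a large-sample approximation, and it is poor when expected counts are small. Here one class is predicted to contribute no positives, so the expected counts of positives rest wholly on how many epileptogenic sites show fast ripples. If that number is small, the approximation is weak just where the primary conclusion is drawn.

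Two things are at stake. One or two positive sites could produce a nominally significant primary result that an exact test would not support. And because the version of chi-square is not stated, the same data could be called significant or not, depending on a choice made after they are seen. Neither problem comes from clustering of sites within patients, which is a separate matter; both remain with one independent site per patient.

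**Working it through.** The plan states no p-value, rate or power figure for this endpoint, so there is nothing of its own to reproduce. The check uses assumed tables, independent sites and a two-sided level of 0.05.

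**1. Formulas.** For *a* positives among n1 epileptogenic sites and 0 among n2 non-epileptogenic sites, with N = n1 + n2:
- Pearson: X² = N·a·n2 / [n1·(N − a)]
- Smallest expected count: a·min(n1, n2)/N
- Fisher, when the observed table is the least probable one: C(n1, a)/C(N, a). With n1 = n2 the mirror-image table doubles this.

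**2. Worked cases.**
- 1/10 v 0/40: X² = 50×1×40/(10×49) = 4.08, p=0.043. With Yates, X² = 50×(40 − 25)²/(10×40×1×49) = 0.574, p=0.45. Fisher = 10/50 = 0.20. Smallest expected count 0.2.
- 2/10 v 0/20: X² = 30×2×20/(10×28) = 4.29, p=0.038. Fisher = 45/435 = 0.10. Smallest expected count 2×10/30 = 0.67.
- 10/25 v 0/25: X² = 50×10×25/(25×40) = 12.5, p=0.0004. Smallest expected count 10×25/50 = 5.

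| Assumed table | Smallest expected | Pearson | Yates | Fisher |
|---|---|---|---|---|
| 1/10 v 0/40 | 0.20 | 0.043 | 0.45 | 0.20 |
| 1/4 v 0/16 | 0.20 | 0.040 | 0.44 | 0.20 |
| 2/10 v 0/20 | 0.67 | 0.038 | 0.20 | 0.10 |
| 4/10 v 0/10 | 2.0 | 0.025 | 0.094 | 0.087 |
| 6/10 v 0/10 | 3.0 | 0.003 | 0.015 | 0.011 |
| 10/25 v 0/25 | 5.0 | 0.0004 | 0.0015 | 0.0006 |

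Fisher's conservatism does not explain the unbalanced rows. Boschloo's unconditional exact test gives 0.24 for 1/10 v 0/40 and 0.097 for 2/10 v 0/20. It does matter for 4/10 v 0/10, where Boschloo gives 0.033, so that row is weak evidence against chi-square.

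**3. When one positive site is enough.** With a = 1 the condition is N·n2/[n1·(N − 1)] > 3.84. At N = 50 this needs n2/n1 > 3.84×49/50 = 3.76: 40/10 = 4.0 passes and 39/11 = 3.55 does not. So epileptogenic sites must be about 20% or less of the total. At 10 v 30 the p-value is 0.079, and at 25 v 25 it is 0.31.

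**4. Type I error of the uncorrected test.** Sum Bin(a; n1, p)·Bin(b; n2, p) over all tables with p-value at or below 0.05, and take the maximum over common rates p from 0.5% to 49.5%:

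| Split | Maximum type I error |
|---|---|
| 10:10 | 4.2% |
| 25:25 | 6.5% |
| 10:20 | 5.2% |
| 10:30 | 5.4% |
| 4:16 | 9.0% |
| 10:40 | 9.1% |
| 10:50 | 7.3% |
| 10:60 | 6.4% |
| 5:45 | 5.1% |

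At 10:40 the peak is at a background rate of 3%, where Fisher's error is 1.2%. Most of the excess is the single table 1 v 0, with probability 10×0.03×0.97⁴⁹ = 0.067. By a 10% background rate the error is back to 4.5%. At 5:45 one positive site is also nominally significant, but that table is too rare to inflate the error: 5×0.02×0.98⁴⁹ = 0.037 near its maximum.

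**The case against.** The strongest reply is that the hypothesis has two halves. It predicts fast ripples in epileptogenic cortex as well as none elsewhere, so the table it leads one to expect has many positives against zero, not one against zero. On such tables the tests agree, even at modest counts (6/10 v 0/10, 10/25 v 0/25). With up to 50 patients and a 64-channel recorder, site counts could be large. A continuity correction is not excluded, and under it none of the first four tabulated cases is significant. Many analysts would also switch to an exact test on seeing small expected counts.

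Much of this stands, and it rules out three stronger readings that a reader might infer:
- *That an empty cell by itself invalidates chi-square.* It does not; small expected counts do.
- *That unequal classes in general nearly double the false-positive rate.* They do not: the maximum is 5.2% at 10:20, 5.4% at 10:30 and 5.1% at 5:45.
- *That one positive site would be significant in this trial.* That needs a split of about 1:4 or more extreme, the uncorrected statistic and a two-sided 0.05 level, none of which the documents give.

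What does not stand is the inference that the plan is therefore safe. There is no minimum enrolment or minimum number of positives; only some electrodes are dual; and section 8 speaks of analysing the data with every patient, so small tables may be examined. A later switch of test is a choice made after seeing the data unless it is written down first.

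**Conclusion.** The point holds conditionally. Section 7b names one large-sample test, version unstated, for a hypothesis in which one class is predicted to have no positives, and it provides nothing for sparse data. If positives are few, the uncorrected p-value can be several-fold too small (0.043 against an exact 0.20 for 1/10 v 0/40; 0.038 against 0.10 for 2/10 v 0/20), and the Pearson and Yates versions can give opposite answers. The type I error reaches about 9% only near a 1:4 split with background rates of a few percent. With equal classes, a smallest expected count of 5 requires at least 10 positive epileptogenic sites (10/2 = 5); above that, little turns on the choice of test.

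These sizes rest on assumed splits, independent sites and a two-sided 0.05 level. The documents do not establish that the trial's tables will be sparse, only that the plan does not guard against it. Because this is the only test named for the primary hypothesis and the repair is small, the change should be made, although a materially wrong conclusion is a possibility and not a forecast.

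**What to change.** In 7b, replace chi-square testing with an exact test fixed before the data are examined:
- Where a patient supplies both epileptogenic and non-epileptogenic sites, use an exact paired test (exact McNemar, if there is one site of each class per patient) or a within-patient permutation test.
- Otherwise use one named exact test, either Fisher's or a stated unconditional test such as Boschloo's. Only one should be named, since they can disagree (0.087 and 0.033 for 4/10 v 0/10).
- State the unit of analysis, the significance level and whether the test is two-sided; the choice between the two branches depends on the unit.
- Report the raw counts and an exact confidence interval for each class beside the p-value. A zero count is then read with its uncertainty: 0/40 has an exact two-sided 95% upper limit of 1 − 0.025^(1/40) = 8.8%.

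The replacement of the test is one sentence, and it changes no study procedure. The price is that exact tests are somewhat conservative, so some p-values will be less favourable than the chi-square value; where positives are plentiful the difference is negligible.

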One system is designed to mimic the original macroelectrode design with the addition of ultra-thin microelectrodes. The original macroelectrode dimensions and properties are retained and additional microelectrodes are positioned at the tip. Leads for the macro and micro electrode recording are separate and are connected to two distinct recording systems. Safety information for the use of the dual electrodes is provided from a single retrospective study of 24 patients who underwent the dual electrode implantation at Mayo Clinic. The complication rate for microelectrodes was 4% compared to 6% for standard electrode systems. Attachment #1 and Attachment #2 address the safety of the electrodes.

The second system (Behnke Fried/Micro Inner Wire Bundle) consists of an outer macro contact depth electrode that accepts delivery of an inner micro wire bundle. The micro contacts extend past the tip of the macro depth electrode.

Data Recording. Recording of iEEG using macroelectrodes has been routinely performed at Dartmouth using the Natus system. Recording of microelectrode potentials will be done using a separate Digital Lynx system or the clinical Natus system. The two systems are distinct and will not share information. The Digital Lynx system is a state-of-the-art microelectrode recording system manufactured by Neuralynx. Neuralynx provides the highest quality microelectrode recording equipment. The Digital Lynx system is not FDA approved for clinical use. However, it has been fully tested and meets the 60601 medical safety standards, has the 60601-1 safety certification for medical devices, and has meets the 60601-2-26 safety standards for EEG equipment. This system is available for clinical use through the lab of [name]. Attachment #3 addresses the safety of the Digital Lynx System.

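### Chi-square is the only method given for the primary fast-ripple comparison, with no unit, alpha or sidedness; on clustered micro contacts its true level could be far from 5% in either direction

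*Combined protocol and SAP*

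**What the plan says.** Section 7a sets the target: "The primary hypothesis is that high oscillations (fast ripples) occur in epileptogenic cortex and are absent in non-epileptogenic cortex". Section 7b then gives the whole analysis for it: "The recording of high frequency oscillations will require only basic statistical analysis using chi-square testing". It does not say whether the counted item is a patient, an electrode, a micro contact, a time segment or an oscillation. It gives no table layout, alpha or sidedness. Section 4 (Data Analysis) adds only that the data go to Matlab, and Section 8 only that each patient's data will be analysed.

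Section 4 (Electrodes) describes the source of the data. In the first system, "additional microelectrodes are positioned at the tip". The second system "consists of an outer macro contact depth electrode that accepts delivery of an inner micro wire bundle". Section 4 (Patient selection) says that "certain standard electrodes will be substituted with the dual micro-macro electrodes during the iEEG recording". Section 3 lists four regions in which a patient may have depth electrodes. On the recorder, Section 4 says: "Data on neuronal discharge characteristics will be recorded using the 64 Chanel Digital Lynx system running Cheetah software".

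**The concern.** An ordinary chi-square test assumes independent observations. Wires at one tip or in one bundle sample nearly the same tissue in the same patient, so their results are likely to be alike. Counting each as a separate observation then overstates the information and rejects a true null too often. A second dependence works the other way. If one patient supplies both tissue types, a shared patient effect cancels in the difference, and a test that ignores the pairing rejects too rarely.

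This is the only test named for the primary hypothesis. While the unit is open, a reader cannot tell how far the p-value is off, or in which direction. The unit could also be chosen after the data are seen.

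**Working it through.** **The plan's own figure.** The only one is enrolment of up to 50 patients (Section 7c). It comes with no rate, alpha or power, so there is nothing to reproduce.

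**Inputs.** From the documents: chi-square (7b), several contacts per tip or bundle (Section 4), at most 50 patients (7c). Assumed, because the documents do not give them: two-sided 5%, m = 8 wires per bundle, one bundle per tissue type per patient supplying that type, and all correlations and rates.

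**Formula.** Let w be the correlation (ICC) within a bundle and b the correlation between a patient's two bundles. Let r be the number of patients with both tissue types divided by the number contributing to one tissue type. The variance of the difference in pooled proportions, relative to independence, is

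DE = 1 + (m − 1)w − r·m·b, and the true level = 2[1 − Φ(1.96/√DE)].

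If half of the patients have both types and the rest split equally, r = 25/37.5 = 2/3.

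| Patients with both types | w | b | DE | True level |
|---|---|---|---|---|
| All (r = 1) | 0.1 | 0 | 1 + 0.7 = 1.7 | 13.3% |
| All | 0.3 | 0 | 1 + 2.1 = 3.1 | 26.6% |
| All | 0.5 | 0 | 1 + 3.5 = 4.5 | 35.6% |
| All | 0.5 | 0.2 | 4.5 − 1.6 = 2.9 | 25.0% |
| All | 0.3 | 0.26 | 3.1 − 2.08 = 1.02 | 5.2% |
| All | 0.1 | 0.1 | 1.7 − 0.8 = 0.9 | 3.9% |
| All | 0.3 | 0.3 | 3.1 − 2.4 = 0.7 | 1.9% |
| All | 0.5 | 0.5 | 4.5 − 4.0 = 0.5 | 0.6% |
| Half (r = 2/3) | 0.1 | 0.1 | 1.7 − 0.53 = 1.17 | 7.0% |
| Half | 0.3 | 0.3 | 3.1 − 1.6 = 1.5 | 11.0% |
| Half | 0.5 | 0.5 | 4.5 − 2.67 = 1.83 | 14.8% |
| None (r = 0) | 0.1, 0.3, 0.5 | any | 1.7, 3.1, 4.5 | 13.3%, 26.6%, 35.6% |

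**Simulation check.** With 50 patients and a 50% rate, a latent-normal simulation gave 14.0%, 26.7% and 36.1% for the first three rows, and 4.2%, 2.0% and 0.7% for the equal-correlation rows with r = 1. A beta-binomial simulation at a 30% rate showed the same two-way pattern.

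**Number of contacts.** With r·b = 0 and w = 0.1 or 0.3, 4 contacts give 8.6% or 15.5%, and 16 give 21.5% or 40.3%.

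**Rare fast ripples.** The hypothesis is that they are absent from one tissue, so a 50% rate is far from the plan's setting. With 2% in both tissues, 50 patients, 8 wires and uncorrelated bundles, the simulated level is about 10% at latent within-bundle correlation 0.3 and about 26% at 0.7. A latent correlation is not on the same scale as the ICC in the table.

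**One yes/no pair per patient.** Treated as independent (50 pairs, 50% rates), the level is 1.3% at latent correlation 0.6 and 3.4% at 0.3.

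**Patient-level alternative.** A within-patient sign-flip test gave 3.1–4.8% in the simulated null cases that had paired patients; it cannot be run where no patient is paired. Its power at 30% versus 2%, 8 wires and latent within/between correlations from 0.3/0 to 0.7/0.3 is 58–90% with 10 patients and 98–100% with 20. With six it is only about 6–26%, and complete enumeration of the sign patterns gave slightly less. The smallest two-sided p is 2/2^n: 0.0625 at n = 5 and 0.031 at n = 6.

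**The case against.** The plan says only chi-square. It does not say Pearson, pooled or contact-level, and McNemar and Mantel-Haenszel tests are also chi-square tests. If each patient contributed one result for one tissue type, an ordinary chi-square could hold its level. This stands: a reader might infer that the plan commits to pooling contacts, and the text does not support that. What can be shown is that the unit is open and that one natural choice would be invalid.

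Several dual electrodes per patient is an inference. It rests on a plural in Section 4 and on the regions listed in Section 3, while Section 4 (Cognitive Tasks) speaks of the implanted region in the singular. No section states or excludes that one patient supplies both tissue types. Clustering of wires within a tip or bundle is firm; the rest is possible.

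The 5% level is a convention used here, since the plan states no alpha. The 64 channels are recorder capacity, not a contact count. The study is departmentally funded and compares no treatments, and Attachment G says that the microelectrode data have little chance of informing the participant's surgery. That limits the severity but does not remove the gap.

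**Conclusion.** The point holds as a conditional one. Section 7b leaves unit, alpha, sidedness and dependence unspecified, and a chi-square on contacts treated as independent would not be assured to hold its level. At an assumed two-sided 5% and 8 wires, the true level is 13–36% when bundles are uncorrelated or no patient has both tissue types. It is 0.6–3.9% when all patients have both and the correlations are equal, and about 10–26% with 2% rates in the rare-event case above.

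A reader might take this as proof that the error rate is inflated, or take 36% as the worst case. Neither follows. The direction depends on the layout, some combinations come out near 5%, and more contacts give larger errors. Every percentage rests on wire counts, correlations and rates that the documents do not give. The item should be fixed; it bears on the scientific conclusion and not on participants' care.

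**What to change.** In Section 7b, make the patient the independent unit:

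- For each patient with both tissue types, compute the difference in the proportion of fast-ripple-positive micro contacts between epileptogenic and non-epileptogenic tissue. Test it with a two-sided within-patient sign-flip permutation test at a stated alpha.
- If a material share of patients supply only one tissue type, use a mixed logistic model with patient and electrode effects, penalised to cope with zero counts. If none supply both, compare patient-level proportions. Set the share that triggers this before looking at the data.
- In the same item, state the unit, how tissue is labelled and what makes a contact positive.

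The change costs a few sentences and a few lines of code, with no new recordings. The p-value may be less favourable, and patients with one tissue type drop out of the paired test. That test cannot reach p < 0.05 with fewer than six non-zero differences, and six patients give little power, so about 20 paired patients is a more realistic aim.

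The documents give two accrual rates. Section 12b says "We think we can enroll 2-3 patients per year", so 20 patients take 20/3 to 20/2, about 7–10 years. Section 16f says "We anticipate that 5-8 patients per year will be recruited to participate in the study", so they take 20/8 to 20/5, or 2.5–4 years. Both are longer if some patients are unpaired.
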